| Informed Consent | √ | | | | | | |
| Demographics/ Medical History | √ | | | | | | |
| Verify Inclusion/ Exclusion Criteria | √ | | | | | | |
| Allocate Study ID Number | √ | | | | | | |
| Concomitant Medication | √ | √ | √ | √ | √ | √ | √ |
| CWIS Patient Questionnaire | √ | √ | √ | √ | √ | | √ |
| Patient Pain Scale | √ | √ | √ | √ | √ | √ | |
| Patient Assessment | | √ | √ | √ | √ | √ | |
| Wound Assessment | √ | √ | √ | √ | √ | √ | √ |
| Photograph Dressing in situ Before Removal | | √ | √ | √ | √ | √ | √ |
| Dressing Change | | √ | √ | √ | | √ | |
| Photograph Wound Before Dressing Application | √ | √ | √ | √ | √ | √ | √ |
| Dressing Performance | √ | √ | √ | √ | √ | √ | |

CONFIDENTIAL AND PROPRIETARY

This document contains information that is confidential and proprietary to Smith & Nephew PLC and Smith & Nephew, Inc. and is intended for use only by Smith & Nephew and its manufacturer. It shall not be reproduced or copied in whole or in part, nor shall the contents be disclosed by any means without prior written permission from Smith & Nephew, nor shall anyone make any use of it that is contrary to the expressed or implied wishes of Smith & Nephew.

| | |
|--|---|
| Study Protocol—Device |  |
| A Prospective, Multi-center, Post-Market Clinical Follow-Up Study to Evaluate the Safety and Effectiveness of ALLEVYN Gentle Border | Number: ALLEV.PMCF.2017.13 |
| | Version: 3.0 |
| | Date: 21 JUN 2019 |
| Page: Page 9 of 90 | |

| Schedule of Events | Key Visits | | | | | Other Visits | |
|---------------------------------|-----------------------|-----------------|------------------|------------------|-------------------------|--------------------------------|--|
| | Visit 1 (Baseline) | Visit 2 | Visit 3 | Visit 4 | End of Study Visit 5 | Routine Dressing Changes | Treatment Discontinuation (before end of study) |
| | Day 0 | Day 7 (+/-3) | Day 14 (+/-3) | Day 21 (+/-3) | Day 28 (+/-3) | | |
| Adverse Event (AE) Assessment | √ | √ | √ | √ | √ | √ | √ |
| Record Device Deficiencies (DD) | √ | √ | √ | √ | √ | √ | √ |
| End of Study /Exit Form | | | | | √ | | √ |

CONFIDENTIAL AND PROPRIETARY

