7.8 WITHDRAWAL

7.8.1 Withdrawal from Treatment

If a subject is withdrawn from study treatment the Treatment Discontinuation Case Report Form (CRF) needs to be filled out. However, the subjects will be followed up to the end of the study for safety assessments until day 28 (\pm 3 days).

Subjects may be withdrawn early from study treatment based on the decision of the investigator. This might include but is not limited to the following reasons:

- Closure of the reference wound
- Worsening condition of reference wound
- If the subject misses two (2) consecutive dressing changes/study visits, interrupting treatment for longer than seven (7) days
- A change in treatment that is clinically warranted
- An adverse event (AE)
- Concurrent illness
- Adverse device effects (ADE)
- Non-compliance (e.g. did not follow instructions)
- Lost to follow-up (LTFU)
- Any other significant reason identified by the Investigator

CONFIDENTIAL AND PROPRIETARY

This document contains information that is confidential and proprietary to Smith & Nephew PLC and Smith & Nephew, Inc. and is intended for use only by Smith & Nephew and its manufacturer. It shall not be reproduced or copied in whole or in part, nor shall the contents be disclosed by any means without prior written permission from Smith & Nephew, nor shall anyone make any use of it that is contrary to the expressed or implied wishes of Smith & Nephew.

| | |
|--|---|
| Study Protocol—Device |  |
| A Prospective, Multi-center, Post-Market Clinical Follow-Up Study to Evaluate the Safety and Effectiveness of ALLEVYN Gentle Border | Number: ALLEV.PMCF.2017.13 |
| | Version: 3.0 |
| | Date: 21 JUN 2019 |
| | Page: Page 32 of 90 |

Any subject that does not meet the minimum reference wound size requirement following wound size tracing at Visit 1 will be withdrawn. Subjects withdrawn from the study for this reason alone shall be replaced by enrolment of a new study subject. A new subject number will be assigned.

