8. STUDY DESIGN

8.1 STUDY DESIGN

This is a non-randomized, open label study in up to 8 study centres at maximum, conducted in up to 3 countries in Europe. The sample size is 40 subjects. There is no comparator group, however, subjects will be consecutively enrolled into 2 wound groups: A minimum of 10 subjects with acute wounds and a minimum of 10 subjects with chronic wounds.

Participation in the study will last 4 weeks (28±3 days) for each subject. All subjects will receive ALLEVYN Gentle Border as the study device, there is no control group. Subjects will be required to make at least one visit per week to the study center.

In total, 5 study visits are planned for each subject (day 0, day 7, day 14, day 21, day 28). The primary clinical endpoint (reduction of wound size) will be assessed at each study visit by using a specific camera. This camera will make a photograph of the wound in a standardized manner and will calculate the wound length, wound width and the depth of the wound automatically.

CONFIDENTIAL AND PROPRIETARY

This document contains information that is confidential and proprietary to Smith & Nephew PLC and Smith & Nephew, Inc. and is intended for use only by Smith & Nephew and its manufacturer. It shall not be reproduced or copied in whole or in part, nor shall the contents be disclosed by any means without prior written permission from Smith & Nephew, nor shall anyone make any use of it that is contrary to the expressed or implied wishes of Smith & Nephew.

| | |
|--|---|
| Study Protocol—Device |  |
| A Prospective, Multi-center, Post-Market Clinical Follow-Up Study to Evaluate the Safety and Effectiveness of ALLEVYN Gentle Border | Number: ALLEV.PMCF.2017.13 |
| | Version: 3.0 |
| | Date: 21 JUN 2019 |
| | Page: Page 33 of 90 |

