9. STUDY PROCEDURES

9.1 VISITS AND EXAMINATIONS

9.1.1 Summary

All subjects receive the ALLEVYN Gentle Border study device at visit 1 (Baseline, day 0). In total, all subjects need to perform 5 key study visits between week 1 and week 4, as shown in table 1. The visit schedule is based on the 7 days of maximum dressing wear time of ALLEVYN Gentle Border. The key visit date is counted from Baseline (day 0) and usually occurs on the same weekday in the following week. If a dressing change is required between the key visits the subject should come to an interim on-site visit (Routine Dressing Change Visit). A routine dressing change assessment will then be performed and documented in the Case Report Form. Then the subject

CONFIDENTIAL AND PROPRIETARY

This document contains information that is confidential and proprietary to Smith & Nephew PLC and Smith & Nephew, Inc. and is intended for use only by Smith & Nephew and its manufacturer. It shall not be reproduced or copied in whole or in part, nor shall the contents be disclosed by any means without prior written permission from Smith & Nephew, nor shall anyone make any use of it that is contrary to the expressed or implied wishes of Smith & Nephew.

| | |
|--|---|
| Study Protocol—Device |  |
| A Prospective, Multi-center, Post-Market Clinical Follow-Up Study to Evaluate the Safety and Effectiveness of ALLEVYN Gentle Border | Number: ALLEV.PMCF.2017.13 |
| | Version: 3.0 |
| | Date: 21 JUN 2019 |
| | Page: Page 35 of 90 |

continues with the next study key visit, counted from Baseline. If a subject is withdrawn from AGB treatment prior to key visit 5, this subject is still regarded as an active study participant. He/she should continue to come to the study key visit to follow-up with patients' safety up to visit 5.

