| 11. Record the total time that the subject spent at the visit (start to finish of wound care procedures). |
|---|

9.1.3 Study Visit 2 (day 7, ±3), Visit 3 (day 14, ±3), Visit 4 (day 21, ±3)

Visits 2 - 4 will be performed as on-site visits, so the subjects need to be present at each key study time point. These visits should take place every seventh (7) day. In case a dressing change is required before day 7, the instructions for a Routine Dressing Change Visit need to be followed (chapter 9.1.4).

Subjects who are already withdrawn from treatment and no longer require a dressing change shall be followed up on the study visits to collect safety information.

- | |
|---|
| 
 1. Question subjects regarding any changes in health or concomitant treatment. 2. Hand out the CWIS, Patient Assessment Scale and Pain Scale to the subject and allow sufficient time to complete it. 3. Photograph the dressing in situ prior to removal with the delivered digital camera. 4. Remove the old dressing and inspect the wound. Complete a wound assessment according to BWAT (see Section 9.2.4). 5. Assess the reason for dressing change, assess the ease of dressing removal and dressing leakage. 6. Record any debridement and the method of debridement, and take a photograph of the wound immediately prior to and following debridement. Note: Photographs are not necessary if the subject was withdrawn from treatment at a previous visit. 7. Redress the wound, if clinically indicated. 8. Record details of all dressings used (e.g. brand, size, etc.) as well as any treatment applied underneath the dressing. |
|---|

CONFIDENTIAL AND PROPRIETARY

This document contains information that is confidential and proprietary to Smith & Nephew PLC and Smith & Nephew, Inc. and is intended for use only by Smith & Nephew and its manufacturer. It shall not be reproduced or copied in whole or in part, nor shall the contents be disclosed by any means without prior written permission from Smith & Nephew, nor shall anyone make any use of it that is contrary to the expressed or implied wishes of Smith & Nephew.

| | |
|--|---|
| Study Protocol—Device |  |
| A Prospective, Multi-center, Post-Market Clinical Follow-Up Study to Evaluate the Safety and Effectiveness of ALLEVYN Gentle Border | Number: ALLEV.PMCF.2017.13 |
| | Version: 3.0 |
| | Date: 21 JUN 2019 |
| | Page: Page 37 of 90 |

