9.1.5 End of Study Visit (day 28, ±3)

The End of Study Visit will be performed as an on-site visit. This should coincide with the normal timing of dressing changes, i.e. seven (7) days.

1. Question subjects regarding any changes in health or concomitant treatment.
2. Hand out the CWIS, Patient Assessment Scale and Pain Scale to the subject and allow sufficient time to complete it.
3. Photograph the dressing in situ prior to removal with the delivered digital camera.
4. Remove the old dressing, inspect the wound and complete wound assessment according to BWAT (see Section 9.2.4).
Note: A full wound assessment is not necessary if the subject has already been withdrawn from treatment.
5. Assess the reason for dressing change, assess the ease of dressing removal and dressing leakage.
6. Record any debridement and the method of debridement, and **take a photograph of the wound immediately prior to and following debridement.**
7. Fill out the Study Completion CRF.

CONFIDENTIAL AND PROPRIETARY

This document contains information that is confidential and proprietary to Smith & Nephew PLC and Smith & Nephew, Inc. and is intended for use only by Smith & Nephew and its manufacturer. It shall not be reproduced or copied in whole or in part, nor shall the contents be disclosed by any means without prior written permission from Smith & Nephew, nor shall anyone make any use of it that is contrary to the expressed or implied wishes of Smith & Nephew.

| | |
|--|---|
| Study Protocol—Device |  |
| A Prospective, Multi-center, Post-Market Clinical Follow-Up Study to Evaluate the Safety and Effectiveness of ALLEVYN Gentle Border | Number: ALLEV.PMCF.2017.13 |
| | Version: 3.0 |
| | Date: 21 JUN 2019 |
| | Page: Page 39 of 90 |

- | |
|---|
| 
8. Record the total time that the subject spent at the visit (start to finish of wound care procedures).
 
9. If any AE or DD are observed or reported, they must be recorded as instructed in Safety Section 12.
 |
|---|

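### After withdrawal for a worsening wound, the day-28 area behind the primary result can be missing, because the photograph instructions conflict

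*Combined protocol and SAP*

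**What the plan says.** **Measurement.** Section 8.1 states: "The primary clinical endpoint (reduction of wound size) will be assessed at each study visit by using a specific camera". Section 9.2.3 takes wound size directly from the Silhouette photographs. It says all subjects are photographed, but refers to section 9.1 for the visit instructions.

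**Schedule.** Table 1 has a row "Photograph Wound Before Dressing Application", ticked at all five key visits, at routine dressing changes and at Treatment Discontinuation. It has no exemption for withdrawn subjects.

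**Withdrawal from treatment.** Section 7.8.1 lists reasons that include "Closure of the reference wound" and "Worsening condition of reference wound". Section 9.1.1 says of a subject taken off the dressing before Visit 5 that "this subject is still regarded as an active study participant", and asks for continued attendance up to Visit 5 for safety follow-up. Section 9.1.3 says that withdrawn subjects who "no longer require a dressing change shall be followed up on the study visits to collect safety information".

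**Instructions after withdrawal.** In 9.1.3 (Visits 2 to 4), a note under the debridement step reads "Photographs are not necessary if the subject was withdrawn from treatment at a previous visit". In 9.1.5 (day 28), a note reads "A full wound assessment is not necessary if the subject has already been withdrawn from treatment".

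**Analysis.** Section 10.4.1 fits a repeated measures ANCOVA and takes the day-28 LSMean in the mITT as the primary result. Section 10.2 keeps a subject in the mITT after one post-baseline assessment. Section 10.1 leaves missing data to a SAP; no such rules are in the supplied text.

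**The concern.** A subject whose wound worsens can be taken off the dressing, keep attending, stay in the mITT, and still have no area at the one time point that gives the primary result. The missing value is then linked to the outcome, because the wounds most likely to be absent at day 28 are those that grew. Leaving them out makes the average reduction look larger.

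The study has a single arm, so no control group shares the error. The hypothesis is a reduction in mean area, and an upward error favours that conclusion. A SAP can choose how to analyse what was collected. It cannot supply the area of a worsened wound that nobody photographed.

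**Working it through.** **1. The plan's own figures.** Inputs from section 11: mean reduction 3 cm², SD 5 cm². Section 10.1: two-sided 5% level. A one-sample t-test with standardised effect 3/5 = 0.6 (noncentral t) gives 83.65% power at n = 26 and 93.16% at n = 35. The stated 83% and 93% reproduce. With 15% lost from 40, 40 × 0.85 = 34 remain, with 92.4% power. The sample size is not in dispute; 34 is used below as the number evaluable.

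**2. Which instruction applies after withdrawal?**

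| Place | Visits 2–4 | Day 28 | At the stop |
|---|---|---|---|
| Table 1 | photograph | photograph | photograph and wound assessment |
| 8.1 | measure | measure | – |
| 9.1.3 | not necessary | – | – |
| 9.1.5 | – | full assessment waived; silent on photograph | – |
| 9.2.3 | defers to 9.1 | defers to 9.1 | – |

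The debridement step is the only wound-photograph step in 9.1.3, and its note waives photographs. The only wound-photograph step in 9.1.5 is also tied to debridement. Because 9.2.3 sends the site to 9.1, it does not settle the conflict in favour of Table 1. A site that reads 9.1 and sees follow-up described as for safety could reasonably take no day-28 photograph.

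**3. What remains for a subject stopped for worsening?** Earlier key-visit areas remain. The 9.1.3 note applies only when withdrawal came at a previous visit, so a stop made at a key visit should still have that visit's area. For a stop between visits, Table 1 asks for a photograph at Treatment Discontinuation. Section 10.4.1 does not say how that area enters a model indexed by visit.

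**4. What remains for a closed wound?** Section 9.2.8 records healed yes/no at each study visit. A healed wound has area 0 cm², so its reduction equals its baseline area. The only thing missing is a sentence saying so.

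**5. Illustrative size, simple observed-case mean.** Let *a* of 34 wounds be lost after worsening, with mean growth *g*, and let the true overall mean reduction be 3 cm². The total reduction is 34 × 3 = 102. Removing wounds with reduction −*g* leaves (102 + *ag*)/(34 − *a*), so the error is

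error = *a*(3 + *g*)/(34 − *a*).

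| *a* | *g* (cm²) | Calculation | Error (cm²) | Share of 3 cm² |
|---|---|---|---|---|
| 1 | 3 | 6/33 | +0.18 | 6% |
| 3 | 1 | 12/31 | +0.39 | 13% |
| 3 | 3 | 18/31 | +0.58 | 19% |
| 3 | 6 | 27/31 | +0.87 | 29% |
| 5 | 3 | 30/29 | +1.03 | 34% |

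The values of *a* and *g* are assumptions. The protocol specifies a model across visits, not this estimator.

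**6. Illustrative size, repeated-measures model.** Simulated trials of 34 wounds, 1,500 per setting:
- Baseline was 3 cm² plus a lognormal amount (median total 6 or 14 cm², log-SD 0.8).
- Day-28 reduction before closure had mean 3 and SD 5, along straight lines or weekly random walks. Measurement noise had SD 0.5 or 1.
- At Visits 2 to 4, wounds that had grown by more than 2, 3 or 5 cm² stopped with probability 0.5.
- The model was fitted by likelihood with unstructured covariance, an assumption because 10.4.1 names no structure.

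With stops for worsening only, 0.5 to 6.2 wounds were lost. Errors against the true day-28 mean:
- observed-case mean: +0.16 to +1.06 cm²;
- model without the area that triggered the stop: 0.02 to 0.72 cm² too high (at most 0.72/3 = 24%);
- model with that area: 0.00 to 0.09 cm² (at most 0.09/3 = 3%).

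Stops between visits were not simulated.

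**The case against.** The best defence is that the protocol, read as a whole, still requires the day-28 photograph. The 9.1.3 note covers Visits 2 to 4 and sits under debridement. Section 9.1.5 repeats the debridement step without that note and waives only the full wound assessment, while Table 1 ticks the photograph at Visit 5. This stands as far as it goes: a reader might infer that the protocol waives the day-28 photograph, and it does not say that. What remains is a conflict between sections, with no explicit instruction to sites for these subjects at day 28.

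A reader might also infer that closed wounds are lost, so that the error could run in either direction. The documents do not support this, because healed status is recorded and the 0 cm² value can be derived. Nor does the row label "Photograph Wound Before Dressing Application" excuse a closed wound on the ground that it gets no dressing. Table 1 ticks that row at Visit 5 and at Treatment Discontinuation, where its Dressing Change row is unticked for everyone.

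Third, section 10 calls itself brief and assigns missing data to the SAP. That is fair for the choice of covariance structure, visit slotting and sensitivity analyses, which are ordinary SAP content. It does not answer the collection gap.

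Finally, photographs after a stop partly measure another dressing, whereas the objective concerns performance over a treatment period. This is a genuine limit on how such areas should be read.

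**Conclusion.** The point holds in a limited form. Sites have conflicting photograph instructions for subjects withdrawn from treatment. Because worsening is a listed reason for withdrawal, the day-28 area can be missing for reasons tied to the outcome, and this would tend to make the mean reduction look too large.

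The size cannot be computed from the documents, which give no stop rates. It would be tempting to quote an error of about 1 cm². That figure needs five wounds lost, or similarly heavy assumed loss, and an observed-case mean that the protocol does not specify. Under a repeated-measures model the illustrative error is at most 0.72 cm² if the area at the stop is left out, and at most 0.09 cm² if it is used. Both depend on the assumed healing paths, stop rule and covariance. Closed wounds need only a derivation rule.

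This is a cheap improvement worth making, held with medium confidence. It does not invalidate the design.

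**What to change.** 1. In 9.1.3, delete the note under the debridement step.
2. In 9.1.5, add a step: photograph the reference wound with the Silhouette camera at day 28 for every subject still attending, whatever the treatment status, as Table 1 already shows.
3. In 10.4.1 or the SAP, state that a wound recorded as healed counts as 0 cm², and that the Treatment Discontinuation area is included in the repeated-measures model.

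**Cost.** One photograph at each remaining key visit, for subjects who are already asked to attend (9.1.1), with a camera already supplied to the site (9.2.3), plus a few sentences of text. Section 11 counts 10 subjects enrolled under version 2.0 as at 19 June 2019, so most of the planned 40 could still benefit when version 3.0 was issued.

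**Downside.** Areas after a stop partly reflect another dressing. Report the last on-treatment area beside the day-28 area so that a reader can see both.

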9.1.4 Routine Dressing Change Visit (between key study visits, if required)

As ALLEVYN Gentle Border has a maximum recommended wear time of 7 days, routine dressing changes might occur between scheduled study visits. **Dressings should not be given to study subjects; the dressing should only be changed by the investigator or delegated person.**

If a subject requires dressing change in between a study visit, the following assessments will be performed.

1. Question subjects regarding any changes in health or concomitant treatment.
2. Ask the subject to assess the comfort of wearing the dressing since the last visit.
3. Photograph the dressing in situ prior to removal with the delivered digital camera.
4. Remove the old dressing, inspect the wound and complete wound assessment according to BWAT (see Section 9.2.4).
5. Assess the reason for dressing change, assess the ease of dressing removal and dressing leakage.
6. Record any debridement and the method of debridement, and **take a photograph of the wound immediately prior to and following debridement.**
7. Assess the level of pain experienced by the subject when the dressing is removed.

CONFIDENTIAL AND PROPRIETARY

This document contains information that is confidential and proprietary to Smith & Nephew PLC and Smith & Nephew, Inc. and is intended for use only by Smith & Nephew and its manufacturer. It shall not be reproduced or copied in whole or in part, nor shall the contents be disclosed by any means without prior written permission from Smith & Nephew, nor shall anyone make any use of it that is contrary to the expressed or implied wishes of Smith & Nephew.

| | |
|--|---|
| Study Protocol—Device |  |
| A Prospective, Multi-center, Post-Market Clinical Follow-Up Study to Evaluate the Safety and Effectiveness of ALLEVYN Gentle Border | Number: ALLEV.PMCF.2017.13 |
| | Version: 3.0 |
| | Date: 21 JUN 2019 |
| | Page: Page 38 of 90 |

8. Redress the wound, if clinically indicated.
9. Record details of all dressings used (e.g. brand, size, etc.) as well as any treatment applied underneath the dressing.
10. If any adverse events or device deficiencies are observed or reported, they must be recorded as instructed in Safety Section 12.
11. Redress the wound with ALLEVYN Gentle Border.
12. Record details of the new ALLEVYN Gentle Border dressing.

9.1.5 End of Study Visit (day 28, ±3)

The End of Study Visit will be performed as an on-site visit. This should coincide with the normal timing of dressing changes, i.e. seven (7) days.

1. Question subjects regarding any changes in health or concomitant treatment.
2. Hand out the CWIS, Patient Assessment Scale and Pain Scale to the subject and allow sufficient time to complete it.
3. Photograph the dressing in situ prior to removal with the delivered digital camera.
4. Remove the old dressing, inspect the wound and complete wound assessment according to BWAT (see Section 9.2.4).
Note: A full wound assessment is not necessary if the subject has already been withdrawn from treatment.
5. Assess the reason for dressing change, assess the ease of dressing removal and dressing leakage.
6. Record any debridement and the method of debridement, and **take a photograph of the wound immediately prior to and following debridement.**
7. Fill out the Study Completion CRF.

CONFIDENTIAL AND PROPRIETARY

This document contains information that is confidential and proprietary to Smith & Nephew PLC and Smith & Nephew, Inc. and is intended for use only by Smith & Nephew and its manufacturer. It shall not be reproduced or copied in whole or in part, nor shall the contents be disclosed by any means without prior written permission from Smith & Nephew, nor shall anyone make any use of it that is contrary to the expressed or implied wishes of Smith & Nephew.

| | |
|--|---|
| Study Protocol—Device |  |
| A Prospective, Multi-center, Post-Market Clinical Follow-Up Study to Evaluate the Safety and Effectiveness of ALLEVYN Gentle Border | Number: ALLEV.PMCF.2017.13 |
| | Version: 3.0 |
| | Date: 21 JUN 2019 |
| | Page: Page 39 of 90 |

- | |
|---|
| 
8. Record the total time that the subject spent at the visit (start to finish of wound care procedures).
 
9. If any AE or DD are observed or reported, they must be recorded as instructed in Safety Section 12.
 |
|---|

